Inclusion criteria -- Participants must:

- be adults (age ≥18)
- report distress associated with being the primary caregiver for a family member with all-cause dementia [23]
 - **[[reporting at least 2 of the following 6 items at baseline assessment: felt overwhelmed, felt like they often needed to cry, were angry or frustrated, felt they were cut off from family or friends, reported moderate to high levels of general stress, or felt their health had declined]]**
- **[[provide at least one hour of care (supervision or direct assistance) per week over the past 3 months (other sources of caregiving for the Veteran with dementia can also be utilized; e.g., respite, home health aide, other family members, etc.)]]**
- be proficient in spoken and written English
- be capable of providing informed consent

Exclusion criteria -- Potential participants will be screened and excluded for:

- current or lifetime history of any psychiatric disorder with psychotic features
- prominent suicidal or homicidal ideation
- having met DSM-IV criteria for drug or alcohol abuse or dependence (except nicotine) within the past six months
- presence of alcohol intoxication (by breathalyzer) or alcohol withdrawal (by exam) during study recruitment or participation
- diagnosis of probable or possible dementia
- a Telephone Cognitive Screen score of < 20
- participation in another caregiver intervention within the past year
- lack of regular access to a telephone
- illness that would prevent 24 months of study participation
- planned transfer of care receiver to another caregiver or nursing home within 12 months

2.A.3.c.1. Recruitment

We aim to recruit 150 participants who meet inclusion/exclusion criteria for the proposed project (ESBR-i: n = 50; ESBR-v: n = 50; UC: n = 50). Participants will be recruited primarily from the VA Palo Alto Health Care System (VAPAHCS), including major divisions (i.e., Palo Alto, Menlo Park, and Livermore) and community-based outpatient clinics (CBOCs) in the surrounding area (i.e., Capitola, Fremont, Modesto, Monterey, San Jose, Sonoma, and Stockton). We anticipate primary referral sources to include: Sierra-Pacific Mental Illness Research Education and Clinical Center (directed by [name]); VAPAHCS Dementia Committee (chaired by [name], consultant); VA Memory Clinic (directed by [name]); Geriatric Research, Education, and Clinical Center ([name], consultant, serves as Clinical Nurse Specialist at this Center); Stanford/VA Aging

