Hypothesis 4. Mixed effects modeling will be used to examine whether participants who receive the intervention via video telehealth (ESBR-v) will show similar levels of caregiver burden compared to those that receive the intervention in-person (ESBR-i) over time. For this exploratory aim, we will focus on monitoring the clinical significance (effect size). We expect the effect size will be quite small (Cohen's *d* of 0.2 or less). In mixed effects analyses, the change in caregiver burden (ZBI total score) will be modeled as the key dependent variable predicted by the group membership (ESBR-i vs. ESBR-v).

Mixed effects modeling will be used to examine whether participants who receive the intervention via video telehealth (ESBR-v) will show similar levels of caregiver depression compared to those that receive the intervention in-person (ESBR-i) over time. For this exploratory aim, we will focus on monitoring the clinical significance (effect size). We expect the effect size will be quite small (Cohen's *d* of 0.2 or less). In mixed effects analyses, the change in caregiver depression (CES-D total score) will be modeled as the key dependent variable predicted by the group membership (ESBR-i vs. ESBR-v).

Mixed effects modeling will be used to test the hypothesis that participants who receive the intervention via video telehealth (ESBR-v) will have similar community tenure compared to those that receive the intervention in-person (ESBR-i) over time. For this exploratory aim, we will focus on monitoring the clinical significance (effect size). We expect the effect size will be quite small (Cohen's *d* of 0.2 or less). In mixed effects analyses, community tenure (time spent living in the community) will be modeled as the key dependent variable predicted by the group membership (ESBR-i vs. ESBR-v).

Cox proportional hazard modeling will be used to test the hypothesis that Veterans with caregivers who receive the intervention via video telehealth (ESBR-v) will show similar rates of LTC placement and survival compared to those that receive the intervention in-person (ESBR-i) over time. In Cox proportional hazard models, LTC placement or survival will be modeled as the key dependent variable predicted by the group membership (ESBR-i vs. ESBR-v).

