We estimated power based on the proposed mixed effects analyses considering the repeatedly measured outcomes. Based on these analyses, we converted the growth model parameter estimated to group difference in primary outcome at 12 month. Considering potentially nonlinear development of our outcomes, we allowed for nonlinear trend over time (specifically, we used a piecewise growth model). In our power estimation for primary hypothesis 1, over the 4 assessments, we assumed the attrition rate of 10% (6 month), 15% (12 month), and 20% (24 month). We assumed the reliability of the Zarit Burden Interview to be 0.7 based on prior studies demonstrating a range of intra-class correlation coefficients that vary based on time intervals between tests [59-61]. Prior studies of caregiver interventions, like many psychosocial interventions, have reported small to medium effect sizes. One such study specifically aimed to improve outcomes of caregivers of Veterans with all-cause dementia of the Alzheimer's type [23] and demonstrated effect sizes (Cohen's *d*) on caregiver burden and depression ranging from 0.26-0.33. Based on this study, we expect an effect size of $d=0.3$ on our primary outcome of caregiver burden, as measured by the Zarit Burden Interview [72], and designed our study to be powered accordingly assuming that mixed effects modeling will be used as the analysis method. Our primary hypothesis (Hypothesis 1) is that those in the intervention group ($n=50$ ESBR-i and $n=50$ ESBR-v) will show steeper decline in burden compared to the usual care ($n=50$ control) group. Under this scenario, the estimated power to detect the difference between the intervention (ESBR-i + ESBR-v) and the control group in terms of care burden is 0.83 ($d=0.3$, $\alpha=0.05$, two-tailed) at the 12-month follow-up. For the secondary analysis, we will monitor both clinical (effect size) and statistical (p -value) significance, with more emphasis on clinical significance, which will inform future trials.

2.A.3.e.9. Implementation Plan

The table below presents a general outline of the activities planned during the award period to ensure timely completion of the research plan, publication/presentation of results, preparation of future studies aiming to enhance Veteran- and family-centered care (i.e., VA Merit Award), and development of a dissemination plan for a successful intervention.

CDA-2 TIMELINE										
	Year 1		Year 2		Year 3		Year 4		Year 5	
Project Component										

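### Hypothesis 4 looks for similarity between video and in-clinic ESBR without a margin or interval criterion, and 50 per arm is too few to exclude a difference of d = 0.2

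*Combined protocol and SAP*

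**What the plan says.** In section 2.A.3.e.8a, under Exploratory Aims, Hypothesis 4 compares ESBR-v with ESBR-i on five outcomes.

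- **Burden and depression.** Mixed-effects models are to examine whether video participants "will show similar levels of caregiver burden compared to those that receive the intervention in-person (ESBR-i) over time". Depression is worded in the same way.
- **Community tenure.** A mixed-effects model is used again, but similarity is now a hypothesis to be tested.
- **LTC placement and survival.** Cox models are to test the hypothesis that Veterans whose caregivers receive video ESBR "will show similar rates of LTC placement and survival compared to those that receive the intervention in-person (ESBR-i) over time".

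For burden, depression and tenure the plan says it will concentrate on effect size, and adds "We expect the effect size will be quite small", with Cohen's d of 0.2 or less in brackets. It gives no expected size for the two Cox outcomes. In every model, arm is the predictor of interest in the usual way. No margin, confidence interval or rule for concluding similarity appears.

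The arm sizes in section 2.A.3.c.1 are "ESBR-i: n = 50; ESBR-v: n = 50; UC: n = 50". Section 2.A.3.e.8b gives power for Hypothesis 1 only. It says "we expect an effect size of $d=0.3$ on our primary outcome of caregiver burden", and that power for the pooled ESBR arms against usual care "is 0.83 ($d=0.3$, $\alpha=0.05$, two-tailed) at the 12-month follow-up". No power or precision is given for Hypothesis 4.

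**The concern.** A model that estimates a difference does not show similarity by failing to find one. With few participants, a small observed d or a non-significant hazard ratio is compatible with a difference that matters. The plan leaves open what result would count as similar, and the one number it offers is an expected point value with no allowance for sampling error. Someone following the text could therefore report that video and in-clinic delivery are similar on data that do not support it. The risk is greatest for tenure, LTC placement and survival, where the wording is that of a hypothesis test. Access by video telehealth is a main reason for the project (sections 2.A.1.E and 2.A.2.d), so readers will look for this comparison.

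**Working it through.** **Inputs from the plan.** 50 per arm; 15% attrition at 12 months; ZBI reliability 0.7; expected pooled effect d = 0.3; two-sided alpha 0.05. Evaluable at 12 months: 50 × 0.85 = 42.5 per arm, so 85 pooled ESBR against 42.5 usual care.

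**Assumption.** The plan gives no residual variance v (in units of the outcome variance), so three values are used: v = 1 (unadjusted); v = 1 − 0.7² = 0.51 (0.7 taken as the baseline-to-follow-up correlation); v = 1 − 0.7 = 0.30 (0.7 taken as the share of variance removed).

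**Step 1: the plan's own power.** For Hypothesis 1, SE = √[v(1/42.5 + 1/85)] and power = Φ(0.3/SE − 1.96).

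- v = 1: SE 0.188, power 0.36
- v = 0.51: SE 0.134, power 0.61
- v = 0.30: SE 0.103, power 0.83

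Only v = 0.30 reproduces the stated 0.83. The plan does not show its formula, so this value is inferred. It serves as the favourable case.

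**Step 2: precision for ESBR-v against ESBR-i.** SE = √(v × 2/42.5); 95% half-width = 1.96 × SE. The last column is Φ((0.2 − 0.3)/SE) − Φ((−0.2 − 0.3)/SE).

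| v | SE | 95% half-width | Upper limit if observed d = 0.2 | Chance that observed d lies within ±0.2 if true d = 0.3 |
|---|---|---|---|---|
| 1 | 0.217 | 0.43 | 0.63 | 31% |
| 0.51 | 0.155 | 0.30 | 0.50 | 26% |
| 0.30 | 0.119 | 0.23 | 0.43 | 20% |

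Every half-width exceeds 0.2, so an observed d of exactly 0 leaves 0.2 inside the 95% interval. Every upper limit exceeds 0.3.

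**Step 3: sensitivity.**

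- *No attrition (50 per arm).* Half-widths are 0.39, 0.28 and 0.215, still above 0.2. The last column becomes 30%, 24% and 18%.
- *Clustering.* Sessions run in groups of up to 10 and no intraclass correlation is given. Assumed values of 0.01 to 0.10 (design effect 1 + 9 × ICC, 1.09 to 1.90) widen the half-width to 0.24–0.32 at v = 0.30 and 0.44–0.59 at v = 1. The last column becomes 21–27% and about 32%.

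**Step 4: power for a formal equivalence claim.** Take a 90% interval and, only because 0.2 is the plan's figure, a margin of 0.2. If the true difference is 0, power with 42.5 per arm is 0 at v = 1 and v = 0.51, and about 3% at v = 0.30. There the 90% half-width is 0.195, so only an estimate within about 0.005 of zero would qualify. For 80% power, n per arm = 2v[(1.645 + 1.282)/0.2]², which is 129 evaluable at v = 0.30 and 429 at v = 1.

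**Step 5: the Cox outcomes.** The plan gives no expected event counts, so no realistic interval can be computed. A bound is possible: if all 100 care recipients in the two ESBR arms had the event, the SE of the log hazard ratio would be about √(4/100) = 0.20. A hazard ratio of 1 would then have a 95% interval of exp(±0.392), or 0.68 to 1.48. Fewer events make it wider.

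**The case against.** The strongest reply is that the aim is labelled exploratory, that for burden and depression it only examines the difference with a focus on effect size, and that such an aim needs no equivalence margin. This stands for an aim of pure estimation and keeps the point minor. It does not cover tenure, LTC placement and survival, where similarity is a hypothesis to be tested. A focus on effect size also makes an interval more necessary.

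A second reply is that an equivalence rule this trial can hardly pass adds little. That is fair, and it is why the main change below is to report intervals and call the aim estimation.

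A reader might also infer four stronger things that the documents do not support:

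- **That the plan has a pass rule of d ≤ 0.2.** The figure is an expectation. The 20–31% above describes what would happen if someone used it as a rule.
- **That such a rule would usually pass a true difference of 0.3.** It would fail it 69–80% of the time.
- **That pooling or roll-out rests on Hypothesis 4.** Pooling for Hypothesis 1 is specified unconditionally (sections 2.A.3.e.8a and 2.A.3.e.8b). The dissemination plan (section 2.A.3.e.10) depends on ESBR proving useful and names no delivery mode.
- **That a difference of 0.3 means video has lost the whole benefit.** The planned 0.3 is for the pooled arms. In-clinic 0.3 and video 0 would pool to 0.15. With a pooled effect of 0.3, a difference of 0.3 means in-clinic 0.45 and video 0.15. A video effect of 0 would then mean a difference of 0.6, which would fall within ±0.2 only about 3% of the time at v = 1, and less otherwise.

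**Conclusion.** The point holds as a minor one about analysis and reporting. Hypothesis 4 looks for similarity with models for a difference and states no criterion for it. On 12-month burden, the 95% half-width is about 0.23 in the favourable case and 0.43 unadjusted, so the data cannot exclude d = 0.2 even at an observed 0, nor 0.3 at an observed 0.2.

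These figures rest on the plan's 15% attrition and on variance values inferred here; the conclusion is the same for all three values and without attrition. They apply to burden only. For depression and tenure no comparable inputs are given, and for the Cox outcomes only the bound in Step 5 is available. There the argument is chiefly one of logic: a non-significant coefficient is not evidence of similarity.

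**What to change.** In section 2.A.3.e.8a, Hypothesis 4:

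1. For every outcome, report the ESBR-v minus ESBR-i estimate, or the hazard ratio, with its confidence interval.
2. For tenure, LTC placement and survival, replace the wording about testing a hypothesis of similarity with wording about estimating the difference.
3. State that similarity will not be concluded from a point estimate or from a non-significant test.
4. If the word *similar* is kept, require the 90% interval to lie inside a margin stated in advance: below 0.3 for d, with a separate margin for hazard ratios. Otherwise report the comparison as inconclusive.

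This changes wording only and needs no extra participants or data. The cost is that the exploratory conclusion will probably be inconclusive. Even at a margin of 0.3, wider than item 4 allows, and a true difference of 0, power with 42.5 per arm is 0 at v = 1, 23% at v = 0.51 and 62% at v = 0.30.
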